8.2.3 Reporting of Serious Adverse Events

8.2.3.1 Immediate Reporting of Serious Adverse Events by Investigator to Sponsor

All SAEs (including SAEs occurring in screen failure and randomized subjects) will be reported to the Sponsor or designee within 24 hours of the Investigator's first knowledge of the event, even if the experience does not appear to be related to duvelisib or ofatumumab, from the time of signing ICF through 30 days after the last dose of study drug.

Serious adverse events should be communicated on an SAE report form as follows:

- Email: [contact]
- Hotline (Phone): [contact] (USA)
- [contact] (USA)
- For international numbers, please refer to the SAE Report Form and supporting documentation.

The initial SAE report must be as complete as possible, including details of the current illness and (serious) AE, and an assessment of the causal relationship between the event and the investigational product(s). Information not available at the time of the initial report (eg, final diagnosis, an end date for the AE, or relevant laboratory values received after the report) must be documented on a follow-up SAE Report Form. All SAE follow-up information must be reported in the same timelines as initial information (ie, within 24 hours of the investigator's first knowledge of information).

At any time after completion of the AE reporting period (ie, 30 days post-treatment), if an Investigator becomes aware of an SAE that is suspected by the Investigator to be related to study drug, the event must be reported as described above.

8.2.3.2 Immediate Reporting of Medical Events of Interest

Reports or laboratory results of **AST or ALT > 3x ULN in combination with total bilirubin > 2x ULN are medical events of interest**, and therefore immediately reportable events, even if the events do not meet serious adverse event criteria.

Clinical findings of **Grade 3 or higher rash are medical events of interest**, and therefore immediately reportable events, even if the events do not meet serious adverse event criteria. Pre-existing skin conditions that recur would not meet this definition unless the recurrence is of a greater severity/frequency than previously experienced.

All medical events of interest will be reported to the Sponsor or designee within 24 hours of the Investigator's first knowledge of the event, even if the experience does not appear to be related to study drug. Medical Events of Interest should be communicated on the SAE / Medical Events of Interest (MEOI) report form, as described above for SAEs.

Any occupational exposure or exposure of an individual not enrolled in the study to the investigational medicinal product must be reported to the Sponsor or designee within 24 hours of the Investigator's first knowledge of the event, even if the exposure does not result in an adverse event. Unintentional exposures should be communicated on the SAE/MEOI report form, as described above for SAEs.

8.2.3.3 Reporting of Serious Adverse Events to the Institutional Review Board (IRBs)/ Ethics Committee

Verastem or designee shall notify the Investigator and/or the IRBs/ECs per institutional guidelines of potential serious risks from clinical trials or any other sources, including the following:

- Suspected adverse reaction that is both serious and unexpected.
- Any findings from other studies that suggest a significant risk in humans exposed to the drug.
- Any finding from animal or in vitro testing that suggest a significant risk to humans exposed to the drug, such as mutagenicity, teratogenicity, or carcinogenicity; or report of significant organ toxicity at or near the expected human exposure.

Verastem or designee shall notify Central Ethics Committees (CEC) of new serious, related, and unexpected AE(s) or significant risks to subjects, per country requirements.

The Investigator will notify Local Ethics Committees (LECs) of serious, related and unexpected AE(s) or significant risks to subjects, per local country requirements.

The Investigator must keep copies of all AE information on file, including correspondence with Verastem or Local Ethics Committees.

8.2.3.4 Reporting of Serious Adverse Events to Regulatory Authorities

Verastem or designee shall notify Regulatory Authorities of serious, unexpected adverse reactions or other adverse events, per local requirements. Expectedness will be determined

using the current duvelisib Investigator Brochure and the ofatumumab United States Package Insert (USPI; 2009) or the Summary of Product Characteristics (SmPC).

8.2.4 Pregnancy and *In Utero* Drug Exposure

Since duvelisib has not been evaluated in pregnant or nursing women, the treatment of pregnant women or women of childbearing potential who are not using effective contraception is contraindicated (see [Section 5.1.1](#) and [Section 6.2.1](#) for instructions on pregnancy testing and birth control).

Pregnancies occurring in subjects or partners of male subjects during the study treatment period until 30 days after the subject's last dose of study treatment are considered immediately reportable events. If a pregnancy occurs in a subject, study treatment must be discontinued immediately. The pregnant woman should be referred to an obstetrician/gynecologist experienced in reproductive toxicity for further evaluation and counseling.

The pregnancy must be reported to Verastem or designee within 24 hours of the Investigator's knowledge of the pregnancy using the Pregnancy Notification Form as follows:

- Hotline (Phone): [contact] (USA)
- [contact] (USA)
- For International numbers, please refer to the Pregnancy Notification Form and supporting documentation.

The Investigator will follow the pregnant woman until completion of the pregnancy, and must notify Verastem of the outcome within 24 hours of the Investigator's knowledge of the pregnancy outcome. The Investigator will provide this information on the Pregnancy Outcome Report Form. This notification includes pregnancies resulting in live, "normal" births.

If the pregnant subject experiences an SAE during pregnancy, or the outcome of the pregnancy meets the criteria for immediate classification as an SAE (ie, spontaneous abortion [any congenital anomaly detected in an aborted fetus is to be documented], stillbirth, neonatal death, or congenital anomaly), the Investigator should follow the procedures for reporting SAEs (ie, report the event to Verastem within 24 hours of the Investigator's knowledge of the event).

All neonatal deaths and congenital anomalies that occur within 30 days of birth (regardless of causality) should be reported as SAEs to Verastem. In addition, any infant death or congenital anomaly occurring after 30 days that the Investigator suspects is related to the *in utero* exposure to the study drug should also be reported to Verastem.

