5.1 ENTRY CRITERIA

5.1.1 Inclusion Criteria

Subjects must meet all of the following criteria:

1. ≥ 18 years of age
2. Diagnosis of active CLL or SLL that meets at least one of the IWCLL 2008 criteria for requiring treatment (Binet Stage \geq B and/or Rai Stage \geq I)
3. Disease that has progressed during or relapsed after at least one previous CLL/SLL therapy
4. Not appropriate for treatment with a purine-based analogue regimen (per NCCN or European Society for Medical Oncology [ESMO] guidelines), including relapse \leq 36 months from a purine-based chemoimmunotherapy regimen or relapse \leq 24 months from a purine-based monotherapy regimen
5. A cytogenetics or FISH analysis of the leukemic cells within 24 months of randomization is required to document the presence or absence of del(17p). Note: if a sample from within 24 months is not available, it should be evaluated as part of the screening laboratory evaluation to inform stratification
6. Measurable disease with a lymph node or tumor mass > 1.5 cm in at least one dimension as assessed by computed tomography (CT)
7. Eastern Cooperative Oncology Group (ECOG) performance status of 0 to 2 (corresponds to Karnofsky Performance Status [KPS] \geq 60%)
8. Willingness by subject to be randomized to receive either ofatumumab or duvelisib at the dose and schedule defined in the protocol
9. Must meet the following laboratory parameters:
 - Serum aspartate transaminase (AST/SGOT) or alanine transaminase (ALT/SGPT) ≤ 3 x upper limit of normal (ULN)
 - Total bilirubin ≤ 1.5 x ULN
 - Serum creatinine ≤ 2.0 x ULN
 - Hemoglobin ≥ 8.0 g/dL with or without transfusion support
 - Platelet count $\geq 10,000$ μ L with or without transfusion support

10. For women of childbearing potential (WCBP): negative serum β -human chorionic gonadotropin (β hCG) pregnancy test within 1 week before randomization (WCBP defined as a sexually mature woman who has not undergone surgical sterilization or who has not been naturally post-menopausal for at least 24 consecutive months [women \leq 55 years] or 12 consecutive months [women $>$ 55 years])
11. Willingness of male and female subjects who are not surgically sterile or postmenopausal to use medically acceptable methods of birth control from the first dose of study drug to 30 days after the last dose of duvelisib and for 12 months after last dose of ofatumumab. Sexually active men, and women using oral contraceptive pills, should also use barrier contraception

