8.2 PROCEDURES FOR ELICITING, RECORDING, AND REPORTING ADVERSE EVENTS

8.2.1 Eliciting and Recording Adverse Events

Subjects will be instructed to report all AEs and will be asked a general health status question at each study visit. All AEs occurring in randomized subjects will be recorded in the eCRF from the time of ICF until 30 days after the last dose of study treatment. An AE will be followed until it is either resolved, has returned to baseline, or is determined to be a stable or chronic condition. All SAEs occurring from the signing of ICF through 30 days post last study drug will be processed as outlined in [Section 8.2.3](#).

At each required visit during the trial, all AEs that have occurred since the previous visit must be reviewed. The Investigator or appropriate designee must determine if the adverse event is serious or non-serious.

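### Pregnancy reporting stops 30 days after the last dose in both arms, although contraception is required for 12 months after ofatumumab, so pregnancies that begin in the intervening 11 months carry no stated duty to notify or follow up

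*Protocol*

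**What the plan says.** Inclusion criterion 11 (Protocol Section 5.1.1, repeated in the synopsis) applies to men and women who are not surgically sterile or postmenopausal. It requires contraception from the first dose "to 30 days after the last dose of duvelisib and for 12 months after last dose of ofatumumab".

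Section 8.2.4 opens with duvelisib and refers the reader to Section 5.1.1 for birth control. It then defines what must be reported at once: "Pregnancies occurring in subjects or partners of male subjects during the study treatment period until 30 days after the" subject's last dose of study treatment. It gives no separate period for ofatumumab. The duties that follow are a notification form within 24 hours of the investigator's knowledge, follow-up ("The Investigator will follow the pregnant woman until completion of the pregnancy"), and an outcome report that extends to uncomplicated births ("This notification includes pregnancies resulting in live" and normal births).

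Two further sentences of Section 8.2.4 deal with bad outcomes. One begins "If the pregnant subject experiences an SAE during pregnancy, or the outcome of the pregnancy meets the criteria for immediate classification as an SAE" and names spontaneous abortion and stillbirth among its examples. The other reads "All neonatal deaths and congenital anomalies that occur within 30 days of birth (regardless of causality) should be reported as SAEs", and is followed by a request for later infant deaths or anomalies that the investigator suspects are related to exposure in utero.

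Outside Section 8.2.4, Section 8.2.3.1 keeps a route open after the 30-day adverse event period "if an Investigator becomes aware of an SAE that is suspected by the Investigator to be related to study drug". In the ofatumumab schedule (Table 4), pregnancy tests are done on treatment, and neither a pregnancy test nor an AE/SAE assessment is marked for the Clinical Assessment Period, Cycles 9 to 19. Section 8.2.1 does say that subjects "will be asked a general health status question at each study visit".

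**The concern.** The protocol treats the year after the last ofatumumab dose as a time when pregnancy should be avoided. It asks for pregnancies to be notified and followed only in the first 30 days of that year. The duvelisib arm has no such mismatch.

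Inside the window, Section 8.2.4 collects every pregnancy, including normal births. Outside it, what remains are routes for certain adverse outcomes. Those outcomes would then have no denominator of exposed pregnancies, and their capture would depend on the site happening to hear of them. The loss is mainly of uncomplicated pregnancies and of prospective follow-up. Only safety data are at stake. PFS, ORR, OS, the type I error and power are untouched.

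**Working it through.** The plan states no figure to reproduce. The check compares two stated windows and then reads Section 8.2.4 to see which duties belong to which window.

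**Length of the gap** (contraception period minus reporting window, both counted from the last dose):

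- Duvelisib: 30 − 30 = 0 days.
- Ofatumumab: 365 − 30 = 335 days, about 11.0 months. As a share of the contraception period, 335/365 = 92% of calendar days. This measures time, not risk.

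**Where the gap falls for a full ofatumumab course.** The 12 doses are three in Cycle 1, four in Cycle 2 and one on Day 1 of each of Cycles 3 to 7. Cycle 1 lasts 21 days and later cycles 28.

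- Last dose, Cycle 7 Day 1: 1 + 21 + 5 × 28 = study Day 162.
- Reporting window ends: 162 + 30 = Day 192.
- Contraception period ends: 162 + 365 = Day 527.
- Day 1 of Cycles 9, 11, 13, 15, 17 and 19 falls 56, 112, 168, 224, 280 and 336 days after the last dose. All six visits lie inside the gap.

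**Which pregnancies are in the gap.** Section 8.2.4 counts pregnancies that occur by day 30, and its 24-hour clock runs from the investigator's knowledge. A pregnancy that began by day 30 and comes to light at the safety follow-up visit (day 30 to 37) or at Cycle 9 keeps every duty. The 335 days concern only pregnancies that begin after day 30.

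**Which duties are tied to the 30-day window.** The notification and follow-up sentences refer back to the pregnancy, or the pregnant woman, just defined. The sentence on SAEs, spontaneous abortion and stillbirth refers back to the pregnant subject in the same way. One reading should serve for all of them, and the natural one ties them all to the 30-day sentence. The neonatal sentence is different because it begins with all such events.

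**What remains for a pregnancy beginning between day 31 and month 12:**

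| Item | Stated duty? |
|---|---|
| Notification form within 24 hours | No |
| Follow-up to completion | No |
| Report of a normal outcome | No |
| SAE in pregnancy, spontaneous abortion, stillbirth | Not under 8.2.4 on the natural reading; under 8.2.3.1 if an SAE suspected to be related |
| Neonatal death, or anomaly within 30 days of birth | Yes (8.2.4) |
| Later infant death or anomaly | Yes, if suspected related (8.2.4) |

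**Whether existing contacts can cover month 12.** Survival contacts are six-monthly, with a margin of 4 weeks, and the first is timed from documented progression or from treatment discontinuation (Section 6.5.3.2). Timed from discontinuation, the second falls at 365 ± 28, or days 337 to 393, so it may come before month 12. Timed from progression, the dates differ again. A question tied to a numbered contact could therefore miss the end of the period.

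**The case against.** The strongest defence is that the 30-day limit is a consistent choice. The same limit governs AE and SAE collection in both arms. Section 8.2.4 is written around duvelisib, which had not been studied in pregnancy, while ofatumumab is an approved comparator given according to its label. Nothing in the documents says that a reporting window must equal a contraception period. The group concerned is also small: Section 1.2.1 gives a median age at CLL diagnosis of 72, with about 10% younger than 55.

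These points reduce the weight of the concern but do not explain the mismatch. Section 8.2.4 sends the reader to the section that contains the 12-month period and gives no reason for ending reporting 11 months earlier.

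It could also be said that the notification and follow-up sentences state no day limit of their own, so they might extend past day 30. That is possible but strained. They describe the pregnancy that the preceding text has just defined.

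Three stronger conclusions are tempting, and the documents do not support them:

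- **That a pregnancy discovered after day 30 is not reportable.** It is, if it began by day 30.
- **That adverse outcomes of late pregnancies go unreported altogether.** The neonatal, later-infant and late related SAE routes remain.
- **That sites would not learn of a late pregnancy.** Ofatumumab subjects without progression or new therapy continue clinic visits to Cycle 19, and Section 8.2.1 asks a general health question at each visit and a review of AEs at each required visit. What is absent is a stated duty to notify and follow the pregnancy once it is known.

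**Conclusion.** The mismatch is real and confined to the ofatumumab arm. For pregnancies that begin after day 30 and up to month 12, about 335 days, the protocol states no duty of notification, follow-up to completion or outcome report, for subjects or for partners of male subjects.

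The number of pregnancies affected cannot be derived. It depends on women of childbearing potential, and men with such partners, among the 150 subjects planned for ofatumumab, and the documents give no count. The PFS assumption cannot supply one, because being progression-free says nothing about who could conceive. Few cases should be expected.

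The conclusion rests on the protocol text and on reading the duties in Section 8.2.4 as tied to its 30-day sentence. The Pregnancy Notification Form with its supporting documents, the consent pages and the protocol of the extension study that some progressing subjects may enter were not available, and any of them could narrow the gap in practice. This is an inexpensive improvement to safety data, not a threat to the trial's conclusions.

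**What to change.** In Section 8.2.4:

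- Set the window to 30 days after the last dose of duvelisib and 12 months after the last dose of ofatumumab, for subjects and for partners of male subjects.
- State that every duty in the section applies over that window: notification, follow-up, outcome report, and the sentence on SAEs, spontaneous abortion and stillbirth.

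In the ofatumumab schedule and survival follow-up, add a question about pregnancy at the existing Clinical Assessment visits and at survival contacts, until one contact falls at or after month 12 from the last dose. The survival contacts are needed because subjects who progress or start other therapy leave the clinic schedule.

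The cost is amendment wording notified to the ethics committees of about 100 sites (Sections 5 and 10.4), a possible consent-form revision (Section 10.2), one added data item, and follow-up of a few pregnancies. No new visits or procedures are needed. An amendment for this alone would be hard to justify, so the change is best carried with another one.

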9 STATISTICAL METHODS

Details of the statistical methods for this study will be documented in a Statistical Analysis Plan (SAP). The SAP may modify the statistical methods outlined in the protocol; however, any major modification will also be reflected in a protocol amendment.

9.1 SAMPLE SIZE

This study employs a randomized, open-label, parallel design to assess the potential superiority of duvelisib treatment over ofatumumab treatment on PFS in CLL or SLL subjects.

The sample size was determined to provide sufficient power to test the primary endpoint of PFS in a group sequential design with one planned interim analysis.

Assuming an exponential distribution for PFS, a total number of 185 PFS events (deaths or progressions) will provide approximately 93% power to detect a hazard ratio of 0.6 (median PFS of 9 months in the ofatumumab group versus 15 months in the duvelisib group) using a one-sided log-rank test at a 2.5% overall significance level (ie, alpha of 0.025). The study design employs the Lan-DeMets spending function for O'Brien-Fleming boundary as the alpha spending function and the Hwang-Shih-DeCani gamma (-4) spending function as the beta spending function. A total of 300 subjects will be randomized in a 1:1 ratio to receive either ofatumumab or duvelisib. Assuming a peak accrual rate of 30 subjects per month with 11 months for accrual ramp-up and a 4% cumulative dropout rate per year, then enrollment would complete in 16 months, with the final analysis for PFS estimated to occur approximately 27.5 months from the randomization of the first subject.

9.2 ANALYSIS SETS

The two most important analysis sets are defined in this section, with additional analysis sets to be defined in the SAP.

9.2.1 Intent-to-Treat Analysis Set

The Intent-to-Treat (ITT) analysis set will include all subjects who were randomized, with treatment group designated according to initial randomization. The ITT analysis set will serve as the primary analysis set for all efficacy endpoints and demographics.

9.2.2 All-treated Analysis Set

The All-Treated (AT) analysis set will include all subjects who received any amount of study drug (duvelisib or ofatumumab), with treatment group designated according to actual study treatment received. The AT analysis set will be the primary analysis set for safety endpoints.

9.3 DISPOSITION, DEMOGRAPHIC AND BASELINE CHARACTERISTICS

A tabulation of subject disposition will be presented, which will include the number of subjects randomized to each treatment, and the number of subjects dosed for each treatment.

Discontinuation from study treatment will be summarized by reason for each treatment group. Discontinuation from study will also be summarized by reason for each treatment group.

Details for the summary of demographic and baseline characteristics will be provided in the SAP.

9.4 EFFICACY ANALYSES

9.4.1 Analysis of Primary Efficacy Endpoint

The primary efficacy endpoint is PFS based on disease status as determined by blinded, independent, central review and will be analyzed using the ITT analysis set.

Censoring of PFS will be performed as detailed in the table below. Additional clarifications will be provided in the SAP as needed.

Table 13: Primary PFS Censoring / Event Methodology

Situation	Date of Event or Censoring	Outcome
No adequate baseline disease status assessment	Date of randomization	Censored
No adequate post-baseline disease status assessment unless death occurs prior to first post-baseline assessment	Date of randomization + 1	Censored
No documented progression or death before data cutoff	Date of last adequate disease status assessment	Censored
Documented progression with ≤ 1 missing scheduled disease status assessment before progression	Date of the earliest assessment that results in a finding of unequivocal progression	Event
Death before progression being documented with ≤ 1 missing scheduled disease status assessment before death	Date of death	Event
Documented progression or death following a long gap between adequate disease status assessments (eg, 2 or more consecutive missed scheduled disease status assessments)	Date of last adequate disease status assessment before the gap	Censored
New anticancer treatment or procedure started before documented progression	Date of last adequate disease status assessment	Censored

Note: Disease status assessment includes CT scans (chest, abdomen and pelvis), bone marrow aspirate and/or biopsy (may not be required of all subjects at all scheduled disease status assessments), CBC and differential count, focused physical examination, disease related constitutional symptoms for disease assessment, and ECOG performance status. An adequate disease status assessment is any disease status assessment for which the blinded independent central review is able to arrive at a disease status (eg, CR, CRi, PR, PRwL, SD, and PD) per protocol-defined criteria.

A stratified log-rank test (1-sided) will be used to compare PFS of the duvelisib arm against PFS of the ofatumumab arm at the interim and final analyses with the overall one-sided significance level controlled at 0.025. The nominal p-value required for statistical significance at an analysis will be calculated based on the numbers of PFS events at all preceding and current analyses. The hazard ratio and the corresponding 2-sided 95% confidence interval (CI) will be estimated using a stratified Cox proportional hazards model. For both the stratified log-rank test and the stratified Cox model, the strata will be those used for stratified randomization, with potential pooling of strata specified in the SAP. PFS will be plotted for each treatment group using the Kaplan-Meier method. Median PFS and its associated 95% CI will be estimated for each treatment group.

Analyses of PFS using other censoring rules will be performed as sensitivity analyses. This will include a worst-comparison case sensitivity analysis in which surviving, non-progressing subjects who were lost to follow-up are treated as being censored at the last adequate disease assessment if they were on the ofatumumab arm, and treated as having an event at the time of the next scheduled disease assessment following the last adequate disease status assessment if they were on the duvelisib arm.

Analyses of PFS will be performed for subgroups of subjects based on selected baseline variables, including stratification factors used for randomization. The details of the subgroup analyses will be provided in the SAP.

